4.3.4 Rationale for Allowing Patients to Continue Treatment until Loss of Clinical Benefit

Conventional response criteria may not adequately assess the activity of immunotherapeutic agents as increase in tumor size does not consistently reflect therapeutic failure (**Wolchok et al. 2009**). The phenomena of pseudo progression or infiltration of tumor by immune cells may mimic tumor progression. Therefore, as this study is evaluating an immunotherapy, the study will allow patients to continue to receive study treatment after documented RECIST v1.1-defined radiographic disease progression, provided the benefit-risk ratio for the patient remains favorable as assessed by the physician and study monitor (see Section 5.3.3).

In the absence of unacceptable toxicity, patients who meet criteria for disease progression per RECIST v1.1 while receiving atezolizumab will be permitted to continue study treatment if they meet all of the following criteria:

- Evidence of clinical benefit, as determined by the investigator following a review of all available data.
- Absence of symptoms and signs (including laboratory values, such as new or worsening hypercalcemia) indicating unequivocal progression of disease.
- Absence of decline in ECOG Performance Status that can be attributed to disease progression.
- Absence of tumor progression at critical anatomical sites (e.g., leptomeningeal disease) that cannot be managed by protocol-allowed medical interventions.

4.4 OUTCOME MEASURES

4.4.1 Primary Outcome Measure

- ORR (PR or CR) per RECIST v1.1.

4.4.2 Secondary Outcome Measures

- Efficacy Endpoints:
 - a. ORR per irRECIST.
 - b. PFS per RECIST v1.1 and irRECIST.
 - c. OS
 - d. DCR per RECIST v1.1 and irRECIST.
 - e. DOR per RECIST v1.1 and irRECIST.

4.4.3 Safety Outcome Measures

- Adverse events per CTCAE v4.0.

4.4.4 Translational Outcome Measures

- Tumor tissue and peripheral blood

4.5 SAFETY PLAN

Patients will be evaluated at each study visit for the duration of their participation in the study (see Section 5.6 and Appendix 1).

Please refer to the atezolizumab and cobimetinib Investigator's Brochures for a detailed description of the safety profile of atezolizumab and cobimetinib.

See Section 6 for complete details of the safety evaluation for this study.

4.6 COMPLIANCE WITH LAWS AND REGULATIONS

This study will be conducted in accordance with current US Food and Drug Administration (FDA) Good Clinical Practices (GCPs), and local ethical and legal requirements.

5. MATERIALS AND METHODS

5.1 PATIENT SELECTION

5.1.1 Inclusion Criteria

Patients will be included in the study based on the following criteria:

- Patients must be informed of the investigational nature of this study and must be willing to give written informed consent in accordance with institutional and federal guidelines. Patients must be able to comply with the requirements and assessments of the study protocol.
- Must have histologically or cytologically documented rare tumor as defined per protocol that is metastatic or locally advanced and unresectable. Patients with locally advanced cutaneous squamous cell carcinoma that are technically resectable but in whom surgery is expected to lead to substantial function impairment or disfigurement are eligible.
- Must be refractory or intolerant to standard lines of therapy.
- Must have completed prior chemotherapy, immunotherapy, or radiation therapy at least 14 days prior to start of treatment and all toxicity must be resolved to CTCAE v4.0 Grade 1 (with the exception of CTCAE v4.0 Grade 2 neuropathy) prior to start of treatment.
- Presence of radiographically evaluable disease.
- Age \geq 18 years

- ECOG performance status ≤ 2
- Tissue Parameters:
 - a. Representative formalin-fixed paraffin-embedded (FFPE) tumor specimens in paraffin blocks (blocks are preferred) or at least 4 unstained slides, with an associated pathology report, for testing of tumor PD-L1 expression (Tumor tissue from bone metastases is not evaluable for PD-L1 expression and is therefore not acceptable).
 - b. Tumor tissue should be of good quality based on total and viable tumor content. Fine-needle aspiration, brushing, cell pellet from pleural effusion, bone metastases, and lavage samples are not acceptable. For core-needle biopsy specimens, at least three cores should be submitted for evaluation.
 - c. Patients who do not have tissue specimens meeting eligibility requirements must be willing to undergo a biopsy during the screening period.
- Adequate bone marrow function as indicated by the following as evidenced by all of the following within 14 days:
 - ANC $> 1000/\mu\text{L}$
 - Platelets $\geq 75,000/\mu\text{L}$
 - Hemoglobin $> 9 \text{ g/dL}$
- Adequate renal function, as evidenced by calculated creatinine clearance $> 30 \text{ ml/min}$ within 14 days prior to enrollment.
- Must have adequate hepatic function as evidenced by all of the following within 14 days prior to enrollment: AST, ALT, and ALP $\leq 3 \times$ institutional upper limit of normal (IULN) without liver mets or $\leq 5 \times$ IULN with liver metastases; and bilirubin $\leq 1.5 \text{ mg/dL}$.
- Able to swallow pills
- Negative serum pregnancy test within 7 days prior to commencement of dosing in premenopausal women. Women of non-childbearing potential may be included without serum pregnancy test if they are either surgically sterile or have been postmenopausal for ≥ 1 year.
- Fertile men and women must use an effective method of contraception during treatment and for at least 5 months after completion of treatment as directed by their physician. Effective methods of contraception are defined as those that result in a low failure rate (i.e., less than 1% per year) when used consistently and correctly (e.g., implants, injectables, combined oral contraception or intra-uterine devices). At the discretion of the Investigator, acceptable methods of contraception may include total abstinence in cases where the lifestyle of the patient ensures compliance. (Periodic abstinence [e.g., calendar, ovulation, symptothermal, post-ovulation methods] and withdrawal are not acceptable methods of contraception.)
- **For individual baskets:**
 - **Appendiceal Adenocarcinoma**
 - Not considered candidate for curative surgery.
 - **Cutaneous squamous cell carcinoma**

- Patients with either metastatic or locally advanced cutaneous squamous cell carcinoma that are technically resectable but in whom surgery is expected to lead to substantial function impairment or disfigurement are eligible.

- **Small bowel adenocarcinoma**

- Must be refractory or intolerant to at least one line of 5FU-based chemotherapy for metastatic disease.

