5.6.1 Informed Consent Forms and Screening Log

Written informed consent for participation in the study must be obtained before performing any study-related procedures (including screening evaluations). Informed Consent Forms for enrolled patients and for patients who are not subsequently enrolled will be maintained at the study site.

All screening evaluations must be completed and reviewed to confirm that patients meet all eligibility criteria before enrollment. The investigator will maintain a screening log to record details of all patients screened and to confirm eligibility or record reasons for screening failure, as applicable.

Re-screening is required if a patient has not met all of the eligibility criteria within 28 days from the original date of the screening visit. Re-screening refers to repeating the entire screening process with the exception of performing a repeat biopsy to collect a tumor tissue sample to be used to determine PD-L1 status and repeating CT and/or MRI imaging scans used for tumor assessment, provided the biopsy tissue sample and imaging scans were obtained during the original screening visit. Patients are only allowed to be re-screened twice. Blood samples may be redrawn due to sample handling problems, breakage, or sample integrity, without being considered a re-screen.

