5.6.5 Tumor and Response Evaluations

Patients will undergo tumor assessments at baseline and every 8 weeks in all cohorts assessed, regardless of dose delays, until radiographic disease progression per RECIST v1.1 or (for atezolizumab treated patients who continue treatment after radiographic disease progression) loss of clinical benefit as determined by the investigator. Thus, tumor assessments are to continue according to schedule in patients who discontinue treatment for reasons other than disease progression or loss of clinical benefit, even if they start new anti-cancer therapy. At the investigator's discretion, tumor assessments may be repeated at any time if progressive disease is suspected.

All measurable and evaluable lesions should be assessed and documented at screening. Tumor assessments performed as standard of care prior to obtaining informed consent and within 28 days prior to initiation of study treatment do not have to be repeated at screening.

Cross sectional imaging will be performed with either contrast enhanced CT or MRI. RECIST 1.1 criteria will be used to determine disease response.

If a CT scan for tumor assessment is performed in a positron emission tomography (PET)/CT scanner, the CT acquisition must be consistent with the standards for a full contrast diagnostic CT scan.

All measurable and evaluable lesions should be re assessed at each subsequent tumor evaluation. The same radiographic procedures used to assess disease sites at screening should be used for subsequent tumor assessments (e.g., the same contrast protocol for CT scans).

Response will be assessed by a blinded radiologist at the MD Anderson Quantitative Imaging Analysis Core using RECIST v1.1 (see Appendix 2) and immune-modified RECIST (see Appendix 5). Assessments should be performed by the same evaluator, if possible, to ensure internal consistency across visits. Results must be reviewed by the investigator before dosing at the next cycle.

For cutaneous squamous cell carcinoma, since “surgery (preferable) or definitive radiation therapy (with or without radiosensitizing agent)” is allowed for patients after initial response, such a definitive local therapy can only be performed after at least 1 tumor assessment.

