Appendix 2 Response Evaluation Criteria in Solid Tumors (RECIST Criteria)

The RECIST criteria should be used to assess response to treatment. Only patients with measurable disease should be entered in the study. Measurable disease is defined as the presence of one lesion that can be accurately measured in at least one dimension (longest diameter to be recorded) as ≥ 2.0 cm with conventional techniques (or as ≥ 1.0 cm by spiral CT). Evaluable lesions should be followed for the assessment of response. Non-measurable lesions include bone lesions, leptomeningeal disease, ascites, pleural/pericardial effusion, lymphangitic carcinomatosis, abdominal masses that are not confirmed by CT, and cystic lesions.

All measurable lesions, up to a maximum of 5 lesions per organ and 10 lesions in total, representative of all involved organs, should be identified as target lesions and recorded and measured at baseline. A sum of the longest diameter for all target lesions will be calculated and reported as the baseline sum longest diameter. The baseline sum longest diameter will be used as the reference by which to characterize the objective tumor response.

- Complete response (CR)
Disappearance of all evidence of tumor for at least two cycles of therapy. Tumor markers must be normal.
- Partial response
At least a 30% decrease in the sum of the longest diameter of target lesions, taking as reference the baseline sum longest diameter.
- Stable disease (SD)
Neither sufficient shrinkage to qualify for partial response nor sufficient increase to qualify for progressive disease, taking as reference the smallest sum longest diameter since the treatment started.
- Progressive disease (PD)
At least a 20% increase in the sum of the longest diameter of target lesions, taking as reference the smallest sum longest diameter recorded since the beginning of treatment or the appearance of one or more new lesions.
- Clinical progressive disease
Patients, who in the opinion of the treating physician investigator have had a substantial decline in their performance status and have clinical evidence of progressive disease may be classified as having progressive disease.

**Appendix 3 National Cancer Institute Common Toxicity Criteria
for Adverse Events**

Version 4 of the NCI-CTC-AE can be obtained from:

<http://evs.nci.nih.gov/ftp1/CTCAE/About.html>

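### The inclusion lists ask only for evaluable disease, but Appendix 2 admits only measurable disease; if the lists alone are followed, patients who can respond only by CR stay in the primary ORR denominator

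*Combined protocol and SAP*

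**What the plan says.** Two current entry rules differ.

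- **Inclusion lists.** The synopsis (General Inclusion Criteria, item 3) and Section 5.1.1 both require "Presence of radiographically evaluable disease". Neither list mentions measurable disease, and Section 5.1.1 does not cite Appendix 2.
- **Appendix 2.** It states "Only patients with measurable disease should be entered in the study". Section 5.6.5 makes this the RECIST v1.1 reference for the blinded reader at the "Quantitative Imaging Analysis Core using RECIST v1.1 (see Appendix 2) and immune-modified RECIST (see Appendix 5").

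Appendix 2 also fixes who can respond.

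- Measurable lesions, "representative of all involved organs, should be identified as target lesions and recorded and measured at baseline", form the target set.
- Partial response (PR) is "At least a 30% decrease in the sum of the longest diameter of target lesions, taking as reference the baseline sum longest diameter".
- CR is "Disappearance of all evidence of tumor for at least two cycles of therapy", which does not depend on target lesions.
- "Non-measurable lesions include bone lesions, leptomeningeal disease, ascites, pleural/pericardial effusion, lymphangitic carcinomatosis" and some further types.

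The primary analysis set in Section 5.10.3 is everyone dosed at least once who has a baseline tumor assessment. Section 5.10.1 analyses ORR in all treated patients. Neither sets a measurability condition. Replacement is provided for patients who are never dosed (Section 5.10.3) and for those who withdraw (Section 5.8).

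**The concern.** The protocol treats evaluable and measurable as different terms: the synopsis methodology and Sections 4.1 and 5.6.5 name them side by side. Those sentences govern what is documented and reassessed, so they do not settle who may enter.

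Section 5.6.1 ties enrolment to the eligibility criteria: "All screening evaluations must be completed and reviewed to confirm that patients meet all eligibility criteria before enrollment". Someone screening from Section 5.1.1 could therefore accept a patient whom Appendix 2 bars. That patient has no target lesion and cannot reach PR, but counts in the ORR denominator once dosed and assessed at baseline. Non-measurable disease can be assessed at baseline, so the baseline-assessment condition does not screen such patients out.

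What is at stake is the meaning of the primary ORR. As an estimate for measurable disease, the population Appendix 2 names, it would be biased downward, and the test against 10% would lose power. As an estimate for all patients with evaluable disease it would not be biased, but no passage says that this is the intended population.

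**Working it through.** **Inputs from Section 5.10.3:** n = 20 per cohort; null rate 0.10; alternative 0.30; one-sided alpha 0.05; exact binomial test; stated power 76%.

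**Assumed, because the documents give no figure:** k, the number of the 20 patients without a measurable lesion, from 1 to 5; q, the CR rate in those patients, at 0, 5% or 10%; ORR of 30% in the measurable patients.

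**Step 1: reproduce the plan.** The critical value is the smallest r with P(X ≥ r | 20, 0.10) ≤ 0.05. At r = 4 the probability is 0.133; at r = 5 it is 0.0432, so r = 5. Power is P(X ≥ 5 | 20, 0.30) = 0.7625, which matches the stated 76%. The Clopper-Pearson interval for 6/20 is (0.119, 0.543), also as stated.

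**Step 2: both rules applied.** Then k = 0, and power is 76.2% at exact alpha 0.043. There is no loss.

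**Step 3: lists alone applied.** With the denominator kept at 20 and the threshold at 5,

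power = Σ over c = 0..k of C(k,c) q^c (1−q)^(k−c) × P(Bin(20−k, 0.30) ≥ 5−c).

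For k = 2, q = 0.10: 0.81 × 0.6673 + 0.18 × 0.8354 + 0.01 × 0.9400 = 0.700.

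| k of 20 | Expected ORR, no CRs: 0.30 × (20−k)/20 | Power, q = 0 | Power, q = 5% | Power, q = 10% |
|---|---|---|---|---|
| 0 | 30.0% | 76.2% | 76.2% | 76.2% |
| 1 | 28.5% | 71.8% | 72.5% | 73.3% |
| 2 | 27.0% | 66.7% | 68.4% | 70.0% |
| 3 | 25.5% | 61.1% | 63.9% | 66.5% |
| 4 | 24.0% | 55.0% | 59.0% | 62.8% |
| 5 | 22.5% | 48.5% | 53.8% | 58.9% |

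**Step 4: type I error.** Set the measurable patients at 0.10 and the k others at q. With k = 5 the error is 1.3%, 2.6% or 4.3% for q = 0, 5% or 10%. At q = 10% all 20 patients respond at the null rate, so the error equals the planned 4.3%; below that it is smaller.

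**Step 5: primary set restricted to measurable patients.** For n = 19, 18, 17, 16 and 15 the critical value remains 5, with alpha 0.0352, 0.0282, 0.0221, 0.0170 and 0.0127. Power is 71.8%, 66.7%, 61.1%, 55.0% and 48.5%, the same as the q = 0 column, because the event (5 or more responders among the measurable patients) is the same. Restriction therefore removes the bias in the estimate but does not restore power.

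**The case against.** The strongest reply is that the two rules are compatible. The lists set a weaker condition and Appendix 2 adds a stricter one, in explicit entry language and in current text. A patient with a lesion measurable on imaging satisfies both, so any harm requires staff to overlook a written rule. This stands, and it makes the loss conditional. It does not remove the defect: the stricter rule sits outside the eligibility section, which does not point to it, and Section 5.6.5 cites Appendix 2 for reading response, not for screening.

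A second reply is that the range for k and q is not anchored in the documents. That also stands. The only power figure the documents support is 76.2%.

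Three stronger readings are tempting but unsupported.

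- **That the stated power is wrong.** It is correct for 20 patients who can all respond at 30%.
- **That the appendiceal cohort will be hit hardest.** Appendix 2 lists ascites as non-measurable, but peritoneal spread is listed only in Appendix 4, which serves the secondary criteria, and no passage gives a frequency. Greater exposure there is plausible but not shown.
- **That replacement is impossible.** Section 5.8 lets the investigator withdraw a patient for reasons beyond those listed and replaces patients who withdraw, which might be stretched to this case. What does hold is that no rule removes a dosed, baseline-assessed patient from the denominator in Section 5.10.3.

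**Conclusion.** The contradiction between the inclusion lists and Appendix 2 is certain; its effect on the primary analysis is conditional. If Appendix 2 is enforced at screening, the effect is zero. If the lists alone are used, power falls as tabulated: by about 6 to 10 points with two such patients of 20 and about 13 to 21 points with four, assuming a 30% ORR in measurable patients and a CR rate of 0 to 10% in the others. The error is conservative as long as that CR rate does not exceed 10%, so a false claim of activity is not the worry; a missed signal and an unclear target population are. The point should be fixed because the text change is small and the design starts from only 76% power.

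**What to change.** **Main change.** In the synopsis and Section 5.1.1, replace the criterion with: at least one radiographically measurable lesion at baseline per RECIST v1.1. This agrees with Appendix 2. Keep the word radiographically. Then:

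- State which measurability definition applies. Appendix 2 uses 2.0 cm by conventional techniques or 1.0 cm by spiral CT; Appendix 4 uses 10 mm by CT or MRI and a 15 mm short axis for nodes.
- State whether skin lesions measured only by caliper, which Appendix 4 accepts, count in the cutaneous squamous cell cohort, given that Section 5.6.5 has response read by a radiologist on cross-sectional imaging.

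**If evaluable-only patients are meant to stay eligible,** amend Appendix 2, define the primary ORR set in Section 5.10.3 as patients with measurable disease at baseline, and restate power for the reduced number (Step 5).

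Replacing such patients is not a good route. They would already have been treated, and if 5% to 25% of entrants were affected, 60/(1 − share) gives 63 to 80 treated patients. That exceeds the planned 60, where the toxicity boundaries in Section 5.10.5 end.

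**Cost.** One criterion in two places and two clarifying sentences. Some candidates may be screened out. If 5% to 25% of those eligible under the present lists lack a measurable lesion (assumed), 20/(1 − share) gives 21.1 to 26.7 candidates per cohort. At 1 to 2 per month this adds 0.5 to 1.1 months at the low end and 3.3 to 6.7 at the high end, against 18 months planned. If the stated accrual rate already counts only measurable patients, the added time is nil.

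Section 4.1 points to Appendix 6 for RECIST v1.1, but that appendix covers adverse-event management. This is a separate clerical correction.

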5.1.2 Exclusion Criteria

- Presence of Brain metastases (unless they have been adequately treated with radiotherapy or surgery and stable for at least 30 days prior to enrollment provided patient is neurologically asymptomatic and without corticosteroid treatment for at least 7 days prior to enrollment).
- Uncontrolled intercurrent illness including, but not limited to diabetes, hypertension, severe infection, severe malnutrition, unstable angina, Class II-IV New York Heart Association (NYHA) congestive heart failure (see Section 18.1), ventricular arrhythmias, active ischemic heart disease, or myocardial infarction within 6 months prior to enrollment.
- History of or evidence of retinal pathology on ophthalmologic examination that is considered a risk factor for neurosensory retinal detachment, central serous chorioretinopathy, retinal vein occlusion (RVO), or neovascular macular degeneration.
- Patients will be excluded from study participation if they currently are known to have any of the following risk factors for RVO:
 - a. Glaucoma with intraocular pressure ≥ 21 mmHg
 - b. Grade ≥ 2 serum cholesterol
 - c. Grade ≥ 2 hypertriglyceridemia
 - d. Grade ≥ 2 or symptomatic hyperglycemia (fasting)
 - e. Grade ≥ 2 uncontrolled hypertension (patients with a history of hypertension controlled with anti-hypertensive medication to Grade ≤ 1 are eligible)
- Active malignancy (other than CRC) or a history of prior malignancy within last 3 years. Adequately treated basal cell or squamous cell skin cancer, in situ cervical cancer, ductal carcinoma in situ, other low grade lesions such as incidental appendix carcinoid, or any other cancer from which the patient has been disease and treatment free for two years are allowed. Prostate cancer patients on active surveillance are eligible.
- Pregnant or nursing patients due to risk of fetal or nursing infant harm. Women/men of reproductive potential who do not agree to use an effective contraceptive method while on study and for at least 6 months after study treatment.
- Exclusion criteria related to study medication (any cancer immunotherapy including CD137 agonists, anti-PD-1, anti-PD-L1, or anti-CTLA4 or any MEK or ERK inhibitor).
- Left ventricular ejection fraction (LVEF) $<$ institutional lower limit of normal or $< 50\%$.
- History or risk of autoimmune disease, including but not limited to systemic lupus erythematosus, rheumatoid arthritis, inflammatory bowel disease, vascular thrombosis associated with antiphospholipid syndrome, Wegener's granulomatosis, Sjögren's

syndrome, Bell's palsy, Guillain-Barré syndrome, multiple sclerosis, autoimmune thyroid disease, vasculitis, or glomerulonephritis

- a. Patients with a history of autoimmune hypothyroidism on a stable dose of thyroid replacement hormone may be eligible.
 - b. Patients with controlled Type 1 diabetes mellitus on a stable insulin regimen may be eligible.
 - c. Patients with eczema, psoriasis, lichen simplex chronicus or vitiligo with dermatologic manifestations only (e.g., patients with psoriatic arthritis would be excluded) are permitted provided that they meet the following conditions:
 - Patients with psoriasis must have a baseline ophthalmologic exam to rule out ocular manifestations
 - Rash must cover less than 10% of body surface area (BSA)
 - Disease is well controlled at baseline and only requiring low potency topical steroids (e.g., hydrocortisone 2.5%, hydrocortisone butyrate 0.1%, flucinolone 0.01%, desonide 0.05%, aclometasone dipropionate 0.05%)
 - No acute exacerbations of underlying condition within the last 12 months (not requiring psoralen plus ultraviolet A radiation [PUVA], methotrexate, retinoids, biologic agents, oral calcineurin inhibitors; high potency or oral steroids)
- History of idiopathic pulmonary fibrosis, pneumonitis (including drug induced), organizing pneumonia (i.e., bronchiolitis obliterans, cryptogenic organizing pneumonia, etc.), or evidence of active pneumonitis on screening chest computed tomography (CT) scan
 - a. History of radiation pneumonitis in the radiation field (fibrosis) is permitted.
- History of HIV infection or active hepatitis B (chronic or acute) or hepatitis C infection.
 - a. Patients with past or resolved hepatitis B infection (defined as having a negative hepatitis B surface antigen [HBsAg] test and a positive anti-HBc [antibody to hepatitis B core antigen] antibody test) are eligible.
 - b. Patients positive for hepatitis C virus (HCV) antibody are eligible only if polymerase chain reaction (PCR) is negative for HCV RNA.
- Active tuberculosis or severe infections within 4 weeks prior to Cycle 1, Day 1, including but not limited to hospitalization for complications of infection, bacteremia, or severe pneumonia
- Treatment with systemic immunostimulatory agents (including but not limited to interferon [IFN] or interleukin [IL]-2) within 6 weeks or five half-lives of the drug (whichever is shorter) prior to Cycle 1, Day 1.
- History of severe allergic, anaphylactic, or other hypersensitivity reactions to chimeric or humanized antibodies or fusion proteins.
- Prior allogeneic bone marrow transplantation or prior solid organ transplantation.
- **For individual baskets:**
 - A. Appendiceal Adenocarcinoma**
 - Must not have clinically symptomatic malignant bowel obstruction.
 - B. Cutaneous squamous cell carcinoma**

- None

C. Small bowel adenocarcinoma

- Must not have clinically symptomatic malignant small bowel obstruction.

